adenoma detection rate (40%). An adenoma detection rate of 40% is an increase of at least 15 percentage points, or a 60% increase, over the national benchmark of 15% to 25%.

Patients and clinics served: Currently the On July 1, 2015, the program was enlarged and institutionalized by Penn Medicine with expansion from 5 to 11 zip codes to include Southwest and South Philadelphia. On January 1, 2021, the program expanded from 11 to 18 zip codes throughout Philadelphia County. Currently patients receiving care at one of 4 Internal Medicine practices located in Philadelphia County participate in the program. Another key goal of Penn Medicine is to expand navigation services beyond Internal Medicine to other types of primary care practices, including 3 Family Medicine practices in Philadelphia County. **As part of the resulting expansion of patients requiring navigation, additional FTE navigation staff will be needed and are requested as part of this Administrative Supplement.** Additionally, a key challenge in scaling this navigation program is identifying patient populations at increased risk of CRC, who may benefit most from timely navigation. While risk stratification guidelines exist to determine who should be prioritized for colonoscopy¹⁰, these require time-consuming chart review and may not be adequately sensitive. Automated machine learning algorithms based on routine EHR data accurately estimate a patient's relative risk of CRC in multi-institutional studies.^{1,11,12}

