CRC risk algorithm: The Penn Predictive Healthcare Group is a Penn Medicine-employed team of data and human factors scientists. Their objective is to use EHR data to develop real-time, automated predictive models for use in inpatient and outpatient care settings to inform clinical care delivery. In collaboration with the Predictive Healthcare Group, we have adapted a previously published EHR-based ML algorithm¹ based on complete blood count records from EHR data, adding additional variables of significance including age, gender, BMI, alcohol and smoking status, and relevant comorbidities to generate a model with good discrimination (AUC 0.73), sensitivity (44%), and specificity (90%) in identifying future risk of CRC or adenoma (**see Fig. 4**). During the period of this award, the Data Science Team will retrain the algorithm in a racially and ethnically diverse subgroup residing and receiving care within Penn Medicine Internal and Family Medicine clinics located in Philadelphia County.

Strategies to Elicit Needs

Given that we are utilizing a central navigator program that exists outside of the clinic and does not require additional clinic staff, in addition to the fact that outcomes will be identified from routine EHR records and not from dedicated research staff within clinics, we do not anticipate that there will be issues implementing this program into our target clinics given our preexisting infrastructure. However, we will take several steps to ensure clinics' feedback prior to Aim 2.

Focus groups: First, to ensure buy-in and feedback of the additional clinics participating in this program, we will conduct focus groups with relevant leadership from each of the 3 new clinics and each of the 4 older clinics.

Figure 3. CRC navigator workflow

[figure not shown]
[figure not shown]

Figure 4. ML algorithm performance in unselected Penn Medicine cohort

Program Director/Principal Investigator (Last, First, Middle): [name]

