Cohort. The cohort will consist of patients residing in 18 zip codes in Western and Southwestern Philadelphia who have primary care providers in 4 Penn Medicine Internal Medicine practices and 3 Penn Medicine Family Medicine Practices. Patients will have had a colonoscopy order placed in the past 6 months and have not scheduled, cancelled, or no-showed to their colonoscopy.

Intervention. This intervention will utilize the existing Penn Medicine CRC patient navigation program; administrative supplement funding will be used to expand the staff from 1.5 FTE to 2.5 FTE. In the revised intervention, we will provide a monthly list of ~300 patients with unfilled colonoscopies, risk-stratified according

Program Director/Principal Investigator (Last, First, Middle): [name]

the ML algorithm and select high-risk criteria.¹⁰ The navigation team will prioritize timely outreach and navigation to high-risk patients according to a script that communicates risk.

Outcome. The co-primary outcomes, measured within 3 months of enrollment, will be (1) enrollment in navigator program (feasibility); (2) completion of colonoscopy or FIT testing; and (3) adenoma detection rate.

Analysis Plan. We will use an intention-to-treat analysis. We will use propensity score matching using clinical and sociodemographic characteristics to create matched cohorts of patients between the intervention participants and historical controls from the same clinics in the year prior. We will then use logistic regression to assess the association between the intervention and the two primary outcomes, adjusted for age, gender, comorbidity, and area-level socioeconomic status.

Statistical Power. A sample of 344 participants (172 per group) will provide >90% power, assuming Type I error rate with a 2-sided α 0.05 and 50% dropout/refusal to participate to navigation, to detect a 20 percentage-point (pp) increase in colon cancer screening completion (40 \rightarrow 60%, SD 20%) in the intervention group.

Work plan and timeline

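### Aim 2 neither requires matching within practice nor lists practice in the outcome model, although only four of the seven practices already had navigation

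*Combined protocol and SAP*

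**What the plan says.** The Analysis Plan under Approach, Aim 2 builds the comparison in two steps.

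- **Matching:** "We will use propensity score matching using clinical and sociodemographic characteristics to create matched cohorts of patients". The variables are not itemised. Controls are "historical controls from the same clinics in the year prior".
- **Model:** "We will then use logistic regression to assess the association between the intervention" and the primary outcomes, "adjusted for age, gender, comorbidity, and area-level socioeconomic status". Practice is not in this list, and nothing is said about how matched pairs are handled.

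The Aim 2 cohort comes from "4 Penn Medicine Internal Medicine practices and 3 Penn Medicine Family Medicine Practices". These two groups have different histories. On the Internal Medicine side, Existing Services (Patients and clinics served) says: "Currently patients receiving care at one of 4 Internal Medicine practices located in Philadelphia County participate in the program". For Family Medicine, the same paragraph gives a goal still to be met: to "expand navigation services beyond Internal Medicine to other types of primary care practices, including 3 Family Medicine practices in Philadelphia County". The focus-group paragraph under Strategies to Elicit Needs draws the same line, referring to "each of the 3 new clinics and each of the 4 older clinics".

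**The concern.** Practice type marks a known difference in what controls were offered. A prior-year control in Internal Medicine belonged to a practice already served by navigators; a prior-year control in Family Medicine did not. Two things follow.

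1. **Confounding by practice mix.** Matching on patient characteristics alone does not ensure that the matched groups hold the same proportion of Family Medicine patients. If the proportions differ, and completion without the new intervention differs by practice type, the gap enters the estimate as if it were an intervention effect.
2. **A blended estimand.** In Internal Medicine the contrast is algorithm-prioritised navigation against existing navigation. In Family Medicine it is navigation against none. A single odds ratio averages the two with weights that the plan does not set.

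The results are meant to support an application for a cluster-randomized trial among primary care practices (Work plan and timeline). What navigation adds in a new practice, as opposed to one already served, is information that application would need.

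**Working it through.** **Inputs from the documents.** 7 practices (4 Internal Medicine, 3 Family Medicine); 172 patients per group; completion 40% in controls and 60% under intervention (Statistical Power). Among eligible patients contacted by the existing program, 50% agree and 80% of those complete (Existing Services), so 0.50 × 0.80 = 40%. Adenoma detection among those screened through the program is 40%.

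**Not in the documents.** Completion by practice type, practice shares in either period, and any within-pair or within-practice correlation. Values for these are assumptions.

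**Step 1: bias from mix.** With no true effect, let f be the Family Medicine share and p the completion rate:

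bias = (f_intervention − f_control) × (p_FM − p_IM)

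Take p_IM = 40% (in line with the figure above), p_FM = 20% (assumed), and shares of 50% and 30% (assumed):

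- intervention: 0.5 × 20 + 0.5 × 40 = 30%
- control: 0.3 × 20 + 0.7 × 40 = 34%
- bias: 30 − 34 = −4 percentage points (pp)

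Other assumed values, with an intervention share of 3/7:

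| Control share | Gap 10 pp | Gap 20 pp |
|---|---|---|
| 30% | −1.3 pp | −2.6 pp |
| 20% | −2.3 pp | −4.6 pp |

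The sign reverses if the Family Medicine share is lower in the intervention group, and the bias is zero if the shares are equal.

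**Step 2: simulation with no true effect.** Each setting had 300 runs: 172 intervention patients (3/7 Family Medicine), a pool of 1,000 controls (20% Family Medicine), and practice types about 0.6 logits apart. Matching was one-to-one on a single covariate, and the model adjusted for that covariate but not for practice. Without matching on practice, the mean log odds ratio was −0.16 with 8% rejection at the 5% level. With exact matching on practice, these were 0.00 and 4%.

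**Step 3: blending.** On the risk-difference scale, the pooled effect is f × Δ_FM + (1 − f) × Δ_IM. Unless the two effects are equal, the answer moves with f, even when the matched groups have identical mix.

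**Step 4: what separate reporting can bear.**

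power = Φ[(0.20 − 1.96√(0.50/n)) / √(0.48/n)]

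- n = 172 analysed per group: 96.3%, consistent with the plan's figure of more than 90%. (Whether the stated 50% dropout or refusal is covered is a separate matter.)
- Family Medicine, if 3/7 of patients (assumed): n = 73.7, z = 0.48, power about 68%.
- Internal Medicine, the remaining 4/7: n = 98.3, z = 0.86, power about 81%.

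For adenomas, 172/7 ≈ 24.6 patients per practice per group. At 40% to 60% completion and 40% detection, that is 24.6 × 0.4 × 0.4 ≈ 4 to 24.6 × 0.6 × 0.4 ≈ 6 cases.

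**The case against.** **Controls come from the same clinics.** This is the best defence, and it may have been meant as clinic-by-clinic sourcing. As written, it limits the pool to the same practices and does not say that each pair shares one. It weakens the concern without removing it.

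**The propensity variables are not listed, so practice might be among them.** This stands. A reader might infer that the plan excludes practice from the score, or that it decides to ignore pairing. The documents are silent on both. Only the outcome model has a stated covariate list, and practice is absent from that.

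**The size is assumed.** This also stands. Nothing in the text supports a 20-point change in mix within a year, and matching on sociodemographic variables might remove part of any shift.

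**Standard errors.** A reader might infer that treating matched patients as independent inflates the standard error materially. With assumed within-pair correlations of 0.05 to 0.20, the unadjusted formula 1/√(1 − ρ) gives 1.026 to 1.118, or 3% to 12%. The documents give no such correlation, and the model adjusts for the kind of variables used in matching. In the simulation without practice differences, pair-clustered and ordinary standard errors were 0.227 and 0.225. Unmodelled practice-by-period variation (assumed SD 0.3 logits) works the other way: the ordinary standard error of 0.224 compared with a true spread of 0.238 with practice matching and 0.253 without. No claim about the size or direction of a standard-error fault is supportable.

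**It is a feasibility study.** True, and it limits the weight of the point. But effectiveness is a stated aim, and the remedy is cheap.

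**Conclusion.** The concern holds as a gap in specification. The plan does not require pairs to share a practice and does not list practice in the outcome model, while its own text shows that access to navigation in the control period differed by practice type. The blending of two contrasts follows from the design and needs no numerical assumption beyond unequal effects.

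The bias is conditional. It requires both a difference in mix between the matched groups and a difference in control completion by practice type. Under the assumed values above it is about 1 to 5 pp, against a planned effect of 20 pp. A reader might infer that the omission would exaggerate benefit, but the documents do not fix a direction: a larger Family Medicine share in the intervention group hides benefit (if control completion is lower there, as assumed), and a smaller one creates it.

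One limit applies to the premise. Prior navigation is described for practices, not for each patient. Coverage grew from 11 to 18 zip codes on January 1, 2021, so some Internal Medicine controls may not have been reached, depending on when the control year falls.

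**What to change.** State the following in the Aim 2 Analysis Plan:

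1. List the propensity-score variables, and match exactly on practice, or on practice type where a practice is too small to supply controls.
2. Add practice (7 levels) to the logistic model. For the sparse adenoma outcome, use practice type instead.
3. Report the effect separately for the 4 existing and the 3 new practices, labelled as descriptive because power within each is limited. Tabulate practice mix in both matched groups.
4. State how pairs are handled. Standard errors clustered on the matched set are a reasonable routine choice; 7 practices are too few for clustering on practice.

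This needs analysis code and a few sentences of text, with no new data collection if practice is recorded with the patient's primary care provider. The drawbacks are that a few patients in small practices may go unmatched and the separate estimates will be imprecise.

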While colorectal cancer screening may reduce cancer-associated mortality, African-Americans in Philadelphia County are over 10 percentage-points less likely to be adherent to colorectal cancer screening guidelines compared to Whites. Despite the proven benefit of regular colonoscopy, CRC screening adherence rates remain only around 50% for Penn Medicine primary care patients. Furthermore, screening rates are consistently worse for African-Americans than White individuals – and this disparity is widening at Penn Medicine (Fig. 2). For this reason, Penn Medicine, a safety net provider for low income, underserved patients in Philadelphia, has instituted a system-wide goal of improving CRC screening for African-American patients.

Existing Services

Colorectal cancer screening navigator program: Adverse social determinants of health such as lack of transportation access contribute to CRC screening nonadherence disproportionately for African-American and other minority communities. Recognizing this, in 2011, Penn Medicine created a navigation program to address poor CRC screening rates and increase access to screening colonoscopies for patients in underserved areas of West, South, and Southwest Philadelphia.² The navigation program provides services to address barriers to cancer screening; these include transportation assistance, detailed instructions on bowel prep, or mailed FIT test for average-risk patients who refuse colonoscopy (see **Fig. 3**). Eligible patients have had a colonoscopy order placed in the past six months and have not scheduled, cancelled, or no-showed to their colonoscopy. Among eligible patients contacted by the navigator program, 50% agree to a colonoscopy over the phone. Of those patients, 80% complete a colonoscopy. The CRC screening navigator program is currently staffed by 1.5 FTE staff, including the nurse lead of the navigator program **[name]**, BSN, RN, OCN (see attached **Letter of Support**) and a part-time clinical assistant. Our prior research has shown that navigated patients have a high rate of colorectal cancer screening completion (79%) and a significantly lower rate of cancelled and/or skipped appointments.² In addition, those who were screened as a result of the program had a much higher

Figure 2. CRC screening in Philadelphia county

Program Director/Principal Investigator (Last, First, Middle): [name]

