Outcome. The primary outcome will be biopsy-proven CRC or adenoma, based on (1) diagnostic or procedural codes for CRC or adenoma using previously published administrative code mappings^{14,15}; and (2) internal datasets on Adenoma Detection Rate (ADR), generated by the Data Analytics Center using Provation and Clarity pathology data. Preliminary data suggest that 4,210 cases of CRC or adenomas exist in our cohort.

Predictors. We will use PennChart Clarity data from the 6 months prior to the colonoscopy as predictors in the model. Predictors will be adapted from prior literature and will include demographic (e.g. age, gender, EtOH history), comorbidity (e.g. anemia, inflammatory bowel disease), laboratory (e.g. hemoglobin, BUN), utilization (e.g. prior colonoscopy orders), and socioeconomic (e.g. area-level income and education) data.^{1,11,12} Additionally, we will use the EPIC social determinants of health tool to extract features such as income, education level, and homelessness that may be associated with CRC risk. .

Modelling strategy. We will compare the cross-validation predicted performance of several ML strategies, including logistic regression, random forest, gradient boosting, and recurrent neural networks, to identify the model with optimal predictive performance. We will report algorithm performance on the hold-out validation set, specifically testing for performance differences between the algorithms. Finally, we will compare performance of the best ML algorithm against an existing PennChart risk stratification model that uses only age and prior colorectal cancer screening utilization as predictors.

Performance metrics. Primary performance metrics will include area under the receiver operating characteristic curve (AUC), area under the precision-recall curve (AUPRC), and sensitivity.

Limitations. Administrative codes and internal ADR data may underestimate the true outcome rate, although the number of cases and event rate (7.0%) should still allow adequate model development.

Aim 2. Pilot testing of ML-facilitated colon cancer screening navigation

Study Design. Prospective cohort study with 3-month enrollment period and 3-month follow-up.

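### Aim 2 leaves prior CRC screening history and race/ethnicity off its stated regression covariates, and its loosely described matching does not guarantee either, so the completion estimate could be biased in either direction

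*Combined protocol and SAP*

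**What the plan says.** The Aim 2 Analysis Plan sets out two steps of adjustment.

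- Matching: "We will use propensity score matching using clinical and sociodemographic characteristics to create matched cohorts". The comparators are "historical controls from the same clinics in the year prior". The individual matching variables are not listed.
- Regression: a logistic model for the association between intervention and outcome, "adjusted for age, gender, comorbidity, and area-level socioeconomic status".

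Three other places bear on the point.

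- Aim 1, Modelling strategy, refers to an "existing PennChart risk stratification model that uses only age and prior colorectal cancer screening utilization as predictors". Aim 1, Predictors, also lists prior colonoscopy orders, under a utilization class kept apart from the demographic, comorbidity, laboratory and socioeconomic classes.
- The section on the need for a cancer control program reports that African-Americans in the county are "over 10 percentage-points less likely to be adherent to colorectal cancer screening guidelines compared to Whites", and says that the disparity at Penn Medicine is widening.
- Aim 2, Cohort, restricts entry: "Patients will have had a colonoscopy order placed in the past 6 months", with that colonoscopy still outstanding.

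**The concern.** Completion of colonoscopy or FIT within 3 months is a co-primary outcome, and the groups come from different calendar periods. The covariates are therefore the only protection against a difference in case mix. It is reasonable to expect that patients who have been screened before differ from those who never have in their readiness to complete a new order. The documents themselves report a racial gap in adherence. Neither variable is in the regression, and the plan does not say that either is in the propensity score.

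The algorithm's risk score is not a substitute. It is built to predict CRC or adenoma, not willingness to be screened, and its predictors come from the 6 months before colonoscopy.

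The result is meant to support an application for a cluster-randomised trial (Work plan and timeline). A distorted completion effect could carry over into that trial's planning.

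**Working it through.** **Reference figures.** The plan gives no figure for confounding, so there is none to reproduce on this point. Its reference values are 40% versus 60% completion (a 20-point effect), 172 per group and two-sided alpha 0.05. With 172 analysed per group, a pooled two-proportion test has 96.3% power for that effect, consistent with the stated figure above 90%. How the 50% dropout allowance enters that figure is a separate question and does not affect what follows.

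**Does the wording of the matching cover these variables?** Aim 1 uses five predictor classes and files prior colonoscopy orders under utilization. The Aim 2 matching names clinical and sociodemographic characteristics only. On the plan's own classification, no utilization class is named for matching. A broader reading of clinical could still include screening history, and sociodemographic could include race. The text neither includes nor excludes them.

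**Size of bias if screening history is left out of both steps.** All inputs are assumptions:

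- d = difference between groups, remaining after matching, in the share with a prior screen: 10 to 20 points
- g = difference in completion between patients with and without a prior screen: 20 to 30 points (for example 50% v 30%, or 55% v 25%)
- bias b = d × g

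With no true effect and 40% completion in controls, the chance of a significant result in the program's favour at n = 172 per group is

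P = Φ[(b − 1.96·s0)/s1], where s0 = √(2·p̄(1 − p̄)/n), s1 = √([0.40×0.60 + p2(1 − p2)]/n), p2 = 0.40 + b, and p̄ is the mean of 0.40 and p2.

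For b = 0.04: p̄ = 0.42, s0 = 0.0532, s1 = 0.0532, so (0.04 − 0.1043)/0.0532 = −1.21 and P = 11.3%. The nominal value is 2.5% in this direction.

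| d | g | b = d × g | share of 20 points | P |
|---|---|---|---|---|
| 10 | 20 | 2 points | 10% | 5.7% |
| 10 | 30 | 3 points | 15% | 8.1% |
| 20 | 20 | 4 points | 20% | 11.3% |
| 20 | 30 | 6 points | 30% | 20.1% |

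A milder case, d = 5 and g = 10, gives 0.5 points and P = 3.1%.

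**Simulation check.** Logistic regression was simulated under no effect (172 per group, 1,500 runs per case, half of patients previously screened on average). Two-sided rejection without and with the covariate was:

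- 7.1% v 5.7% for d = 10, g = 20
- 11.1% v 4.1% for d = 20, g = 20
- 20.9% v 5.3% for d = 20, g = 30

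The simulation has no matching step and only one confounder, so the return to about 5% is built in. It confirms the arithmetic and says nothing about how likely the inputs are.

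**Direction.** If previously screened patients are more common among controls, the sign reverses. A true 20-point gain would then appear as 20 − 2 = 18 down to 20 − 6 = 14 points.

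**Race.** The only documented figure is the adherence gap of over 10 points. If a 10-point gap carried over to completion of an outstanding order (an assumption), a 10 to 20 point shift in racial mix would give 0.10 × 0.10 = 1 point to 0.20 × 0.10 = 2 points.

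**The case against.** The strongest reply is that the regression is the second of two steps. Screening history is naturally a clinical characteristic, and sociodemographic ordinarily covers race. Either could be in the propensity score, with controls drawn from the same clinics. This stands as a limit on the claim. A reader might infer that any difference in past screening would be counted as a program effect. The documents support only that it could be, if the variable is also missing from the matching.

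Three further limits stand.

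- **Prediction of completion.** A reader might take it as established that prior screening predicts completion. The documents use it to stratify CRC risk and nowhere link it to completing an open order.
- **Imbalance between periods.** None is reported. The shared requirement of a recent unfilled order narrows differences in recent behaviour if controls meet it too, which the plan does not say; it does not equalise earlier history. The extension to 18 zip codes and to Family Medicine practices is a reason not to take the periods as alike, but is not evidence of a difference in these variables. The risk ranking does not clearly supply an imbalance either. Under intention-to-treat it sets the order of outreach within the list, and it would select patients only if participants means those reached.
- **Race.** The reported gap is county-wide and says nothing about a change in racial mix between periods.

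The study is also a one-year feasibility project. That lowers the stakes, but the comparison is still planned and powered as an effectiveness estimate.

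**Conclusion.** The point holds in a limited form. The stated regression covariates omit two relevant baseline variables, and the matching description does not secure them. This is more than missing detail, because the regression list as written leaves them out.

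Under the assumed range (10 to 20 point imbalance remaining after matching, 20 to 30 point completion gap) the bias is about 2 to 6 points, or 10% to 30% of the planned effect. It could be smaller, and it is nil if the matching balances both variables or the periods do not differ. The direction is unknown. A reader might infer that the omission necessarily inflates the result or could explain a 20-point gain. The documents do not support the first, and the arithmetic does not support the second under these inputs.

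**What to change.** In the Aim 2 Analysis Plan, list the propensity score variables. Add prior CRC screening utilization and race/ethnicity both to that list and to the regression covariates. Report balance on both after matching, for example as standardised differences.

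Exact matching on ever-screened status, time since last screen and number of earlier unfilled orders are optional refinements. The documents do not show that such derived fields are complete for both groups.

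The cost is a sentence or two in the plan and a small amount of extra EHR extraction for both groups. An existing PennChart model already uses prior screening utilization, so no new patients or new data collection should be needed. The resulting estimate may be less favourable to the program.

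### The Aim 2 power statement uses an SD of 20% that does not fit a yes/no outcome at 40% or 60%, and its >90% power depends on how the 50% refusal enters, which is not stated

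*Combined protocol and SAP*

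**What the plan says.** All of the relevant text is in the Aim 2 part of the Approach.

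- **Statistical Power:** "A sample of 344 participants (172 per group) will provide >90% power", at two-sided alpha 0.05, allowing for "50% dropout/refusal to participate to navigation, to detect a 20 percentage-point (pp) increase in colon cancer screening completion". The rates are 40% and 60%, followed by "SD 20%) in the intervention group".
- **Analysis Plan:** "We will use an intention-to-treat analysis". Propensity scores are used to form "matched cohorts of patients between the intervention participants and historical controls from the same clinics in the year prior", and the outcomes are then analysed by logistic regression.
- **Outcome:** the co-primary outcomes include "enrollment in navigator program (feasibility") and completion of colonoscopy or FIT within 3 months.
- **Intervention and Study Design:** "we will provide a monthly list of ~300 patients with unfilled colonoscopies"; "Prospective cohort study with 3-month enrollment period and 3-month follow-up".

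Two other sections bear on the point. Existing Services reports that 50% of contacted patients agree to colonoscopy and 80% of those complete it. Strategies to Elicit Needs says that outcomes come from routine EHR records.

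**The concern.** Two things in the power paragraph do not fit the rest of the plan.

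First, a binary outcome has no free SD. Once the rates are set at 40% and 60%, the variance is fixed, and it is not the one stated.

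Second, the sentence names 50% refusal but does not say what it does to the calculation. It could mean that 172 is a recruited number of which half are analysed. It could mean that 172 are analysed and 60% already averages over refusers. Or it could mean that 60% is expected only among those who accept. The Analysis Plan adds to the doubt: it matches controls to intervention participants, while the power sentence describes refusal as declining to participate. Read together, these could drop refusers from the intervention group only. Willing patients would then be compared with unselected historical controls, which is not intention-to-treat.

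The study is meant to supply preliminary data for a larger trial (Work plan and timeline). A non-significant completion result would be judged against the claimed power, so the reader must know the conditions under which that power holds.

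**Working it through.** **Inputs (Aim 2, Statistical Power):** 172 per group; two-sided alpha 0.05 (z = 1.960); control 40%; intervention 60%; SD 20%; refusal 50%. For 90% power, z = 1.282.

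**1. SD of the outcome.** sqrt(0.4 × 0.6) = 0.490, the same at 60%. A yes/no variable has an SD of 20% only at a rate of about 4% or 96%.

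**2. Do the inputs give 172?** For 90% power:
- Stated SD: standardised effect 20/20 = 1.0. A two-sample t-test needs 22.02, so 23 per group; 23/0.5 = 46 after 50% loss.
- Binomial variance: n = [1.960 × sqrt(2 × 0.5 × 0.5) + 1.282 × sqrt(0.4 × 0.6 + 0.6 × 0.4)]² / 0.20² = 129.25, so 130 per group; 130/0.5 = 260 after 50% loss.

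Neither route gives 172.

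**3. Does 172 per group give >90%?** Power = Φ[(d − 1.960 × s0)/s1], where d is the difference in rates, s0 the pooled standard error and s1 the unpooled one. With all 172 per group analysed at 40% v 60%:
- s0 = sqrt(0.5 × 0.5 × 2/172) = 0.0539
- s1 = sqrt(0.48/172) = 0.0528
- Φ[(0.20 − 0.1057)/0.0528] = Φ(1.786) = 96.3%

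So the claim reproduces on this reading. The arcsine, unpooled and continuity-corrected versions give 96.2%, 96.6% and 95.3%.

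**4. Other readings of the 50% refusal** (same formula):

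| Reading | Numbers analysed | Rates | Power |
|---|---|---|---|
| 60% is the whole-group rate | 172 v 172 | 40 v 60% | 96% |
| Refusers leave the intervention group only | 172 v 86 | 40 v 60% | 86% |
| Half are lost from both groups | 86 v 86 | 40 v 60% | 75% |
| 60% in acceptors, refusers at 40% | 172 v 172 | 40 v 50% | 46% |
| As the row above, with 172 the number left after refusal | 344 v 344 | 40 v 50% | 75% |

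The diluted rate is 0.5 × 60% + 0.5 × 40% = 50%. The refusers' 40% is an assumption; the documents give no figure. With acceptors still at 60%, refusers at 30% give 45% overall and about 15% power; refusers at 50% give 55% and 80%.

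**5. Break-even.** With 172 per group and a 40% control rate, 90% power needs a whole-group rate of 57.4%. With half refusing and refusers assumed at 40%, acceptors must reach (57.4 − 20)/0.5, about 75%. If acceptors complete at the existing program's 80%, the whole-group rate is 0.5 × 80% + 0.5 × 40% = 60%, and power is 96%. The 80% figure is for colonoscopy alone, so carrying it over is also an assumption.

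These figures ignore matching and covariate adjustment, for which the documents give no inputs.

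**The case against.** The best defence is that the conclusion is true. With the correct variance, 172 exceeds the 130 needed, and the power is 96%. The rise is stated for the intervention group, not for acceptors; the analysis is called intention-to-treat; and enrollment in navigation is an outcome in itself, which makes sense only if non-enrollers are counted. On that plain reading, the wrong SD does no harm, and this is a one-year feasibility study.

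Most of this stands: it is the reading the text favours. It does not remove the point, because the same sentence assumes 50% refusal, gives it no place in the calculation, and yields 172 on no route from its stated inputs.

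Some stronger readings are tempting, and the documents do not support them:
- *344 is too few.* The power is below 90% only on readings that the plan does not adopt.
- *An SD of 20% is impossible for any yes/no outcome.* It is ruled out only at the stated rates. If it describes something else, such as clinic-level rates, the text does not say so.
- *172 came from a t-test at effect 0.5*, which needs 86 per group, and 86/0.5 = 172. The match is exact, but that effect means 10 points over SD 20% or 20 points over SD 40%. Neither is stated, so the origin is a guess.
- *The existing program shows that 60% is out of reach*, since 50% × 80% = 40% of contacted patients. That counts only colonoscopies after agreement; it leaves out FIT and any completion among refusers.

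A further objection concerns the remedy. Defining the intervention group as patients offered navigation would condition that group on being reached, with no such condition on historical controls. This is right, and the fix avoids it.

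**Conclusion.** The point holds as a matter of correction and clarity, and should be fixed. The stated SD is wrong for this outcome (20% against 49%), and the inputs do not reproduce 172 per group. The claim of more than 90% power is correct, at 96%, provided that all 172 per group are analysed and 60% is the whole-group intention-to-treat rate. It is not correct if the 50% refusal shrinks the analysed numbers (86% or 75%) or dilutes the effect (46%, with refusers assumed at 40%). A reader might infer that the study is underpowered; the documents do not show that. They show a power figure whose main condition is unstated.

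**What to change.** 1. **Statistical Power:** delete the SD of 20% and use the binomial variance.
2. **Statistical Power:** enter the 50% refusal explicitly. Say whether 172 is before or after refusal, and whether 40% and 60% are whole-group intention-to-treat rates. If they are, state 96% power with 172 per group analysed, and that 90% needs a whole-group rate of at least about 57.4%. If they are not, give the lower power that applies, with the completion rate assumed for refusers.
3. **Analysis Plan:** replace intervention participants with all patients who meet the Aim 2 cohort definition and are placed on the monthly navigation lists, whether or not they are reached or accept. Select historical controls by the same eligibility definition, and take outcomes from the EHR for everyone. Do not condition the intervention group alone on being offered or accepting navigation.

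About 300 patients a month for 3 months is up to 900 listings, possibly with repeats and with patients never contacted. The text should therefore say how 172 relates to the lists, and the whole-group rate must allow for patients not reached as well as refusers.

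The cost is protocol wording and keeping the monthly lists as the record of who is in the group. EHR outcomes are already planned. The sample size and the use of propensity matching do not change. The downside is a possibly less favourable stated power.
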